8.2.11. Circulating Hormones

To investigate the effect of the study medication on circulating gut hormone levels, all subjects of the study will undergo a fasting blood draw before the first dose, and 1h and 2h after the first dose on day 1 for measuring fasting circulating levels of the following gut hormones: GLP-1 (total and active), CCK, PYY, amylin, GIP (total and active), ghrelin, leptin, and adiponectin (Table 1).

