1.2. Schema

1.3. Schedule of Assessments, Time Points, and Window Allowance

Details on procedures and timing of assessments are presented in [Table 1](#).

Table 1 Schedule of Assessments

Period	Screening	Run-in Visit	Treatment Period (±3 days)			Follow Up/End of Study
			Study Days	-42 to -15	14 days prior to Day 1	
Informed Consent	X					
Inclusion/Exclusion Criteria	X					
Demographics	X					
Medical History	X					
Physical Examination ^a	X		X	X	X	X
Vital Signs	X		X	X	X	X
12-lead ECG	X		X		X	
Hematology	X		X ^b			X
Comprehensive Serum Chemistry	X		X ^b	X	X	X
Urinalysis	X		X ^b	X	X	X
Urine Toxicology	X					
Coagulation Parameters	X					
Pregnancy Test ^c	X		X ^b			X
TSH	X					
Weight/BMI	X	X	X	X	X	X
Height	X					
Fasting Glucose		X				X
HbA1c	X				X	
Waist Circumference			X	X	X	X
Fasting Blood Lipids		X			X	
Fasting Circulating Hormones ^d			X			
Bioimpedance			X	X	X	

Period	Screening	Run-in Visit	Treatment Period (±3 days)			Follow Up/End of Study
			Study Days	-42 to -15	14 days prior to Day 1	
MRI PDFF + Full Body Composition Scan		X			X	
Mixed Meal Tolerance Test (MMTT)		X			X	
Study Drug Dispensation			X ^e			
Concomitant Medication	X		X	X	X	
Indirect Calorimetry		X			X	
Adverse Event Monitoring	X		X	X	X	X
CGM Placement		X		X		
CGM Removal and Download			X		X	X
Fecal Sample Collection ^f		X			X	
Phenotypic Bitter Taste Test ^g		X				
Control of Eating Questionnaire (CoEQ)	X		X	X	X	X

- a. Complete physical examination at screening, and brief physical examination for all follow-up visits
- b. This procedure is not needed if performed within 3 days
- c. For women of child-bearing potential only
- d. GLP-1 (total and active), CCK, PYY, amylin, GIP (total and active), ghrelin, leptin, and adiponectin in all subjects at 3 time points (before the first dosing and 1h as well as 2h after the first dosing)
- e. A single oral dose of oral ARD-101 will be administered to subjects in the morning of day 1
- f. Fecal sample to be collected during run-in visit and on day 28. Optional for subjects
- g. Phenotypic bitter taste test is optional for subjects

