3.1. Primary Endpoint

- The percent total weight change at the end of treatment from baseline

3.2. Secondary Endpoints:

- Safety of ARD-101 by assessment of the incidence of TEAE
- The change in blood lipid concentrations (total cholesterol, triglyceride, high density lipoprotein cholesterol, and low-density lipoprotein cholesterol) at the end of treatment from the baseline
- The change in waist circumference at the end of treatment from the baseline as well as 14 days after end of treatment
- The change in HbA1c at the end of treatment from the baseline

3.3. Exploratory Endpoints:

- Categorical weight loss. Proportion of subjects who lose $< 5\%$ and $\geq 5\%$ of initial weight
- Fasting circulating levels of GLP-1 (total and active), CCK, PYY, amylin, GIP (total and active), ghrelin, leptin, and adiponectin before the first dosing, and at 1h and 2h after the first dosing on day 1
- Changes in response to the MMTT, including:
 - Serum levels of glucose, insulin, and C-peptide prior to (negative timepoints) and post (positive timepoints) the Ensure meal given for MMTT at baseline (run-in visit) and on day 28
 - Serum level of FFA prior to (negative timepoints) and post (positive timepoints) the Ensure meal given for MMTT at baseline (run-in visit) and on day 28
 - Circulating levels of GLP-1 (total and active), CCK, PYY, amylin, GIP (total and active), glucagon, and ghrelin prior to (negative timepoints) and post (positive timepoints) the Ensure meal given for MMTT at baseline (run-in visit) and on day 28
 - Circulating cytokines and inflammatory markers such as CRP at run-in visit and end of treatment (day 28) performed during the MMTT
 - Circulating levels of bile acids, ferritin, leptin, and adiponectin at run-in visit and end of treatment (day 28) performed during the MMTT

- Body composition as measured by bioelectrical impedance scale
- Body composition and hepatic steatosis by MRI-PDFF + full body composition scan pretreatment and end of treatment
- The change in HOMA-IR at the end of treatment from the baseline
- The change in fasting blood glucose at the end of treatment from the baseline
- Hunger and control of eating as measured by Likert and visual analogue scales, respectively
- Change in indirect calorimetry
- The fecal samples will be collected during the run-in visit and on day 28 for microbiome analysis to evaluate potential effects of the study medication on fecal microbiome profile (optional for subjects)

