4. STUDY DESIGN

4.1. Overview

This is a Phase 2, open label study of ARD-101 in subjects with unsatisfactory weight management at least one year after bariatric surgery (sleeve gastrectomy or gastric bypass).

This study has a planned enrollment of 30 subjects (approximately 15 for each preceding surgical procedure) and will be conducted in a single center in the United States.

The study will consist of a Screening Period (up to 28 days), a Run-in Visit Period (up to 14 days), a Treatment Period (28 days), and a Follow-up Period (EOS Visit within 14 days after receiving the last dose of ARD-101). The screening procedures will be initiated upon completion of the informed consent process. Following completion of screening procedures and confirmation of eligibility, subjects will be enrolled to receive ARD-101.

ARD-101 will be administered orally under fasting conditions (approximately 60 minutes **before** breakfast and approximately 60 minutes **before** dinner) at 200 mg BID for 28 days. Subjects will receive treatment in an outpatient setting and will be instructed to visit the clinical center periodically as scheduled in Table 1 for safety and efficacy assessments. The treatment may be discontinued due to intolerable toxicity, withdrawal of informed consent, discretion of principal investigator or end of the study.

All available safety and tolerability data will be evaluated throughout study conduct. Pharmacodynamic data will be analyzed after study completion.

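### On Day 1 the dose-to-breakfast interval in section 4.1 and the fasting hormone draw 2 hours after the dose cannot both be met, and nothing in the plan says which governs

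*Combined protocol and SAP*

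**What the plan says.** Section 4.1 (Overview) states the regimen for the whole treatment period: "ARD-101 will be administered orally under fasting conditions (approximately 60 minutes" ahead of breakfast, and the same interval ahead of dinner. No day is exempted.

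Section 8.2.11 (Circulating Hormones) requires a "fasting blood draw before the first dose, and 1h and 2h after the first dose on day 1", and says the samples are "for measuring fasting circulating levels of the following gut hormones": GLP-1, CCK, PYY, amylin, GIP, ghrelin, leptin and adiponectin. Its stated purpose is "To investigate the effect of the study medication on circulating gut hormone levels". Section 3.3 lists the same fasting levels as an exploratory endpoint, "before the first dosing, and at 1h and 2h after the first dosing on day 1". Table 1 carries a row for fasting hormones on Day 1, and footnote d repeats the draws "at 3 time points (before the first dosing and 1h as well as 2h after the first dosing".

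Table 1 footnote e says only that the first dose is given in the morning of Day 1. No section says when breakfast is eaten that day, or asks for the time of first food. Sections 9.5 and 9.6 list dates and times of drug administration only.

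**The concern.** Two stated rules apply to the same two hours of the same visit and are incompatible. Under one of them, the second post-dose sample is no longer what the endpoint says it is.

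This matters because the draws are meant to attribute a hormone change to the drug. Section 2.1 reports GLP-1 and CCK release by a denatonium salt, and section 6.9.1 gives secretion of both as a route by which ARD-101 may reduce appetite. Food is a competing stimulus by the protocol's own account: section 8.2.7 describes the mixed meal test as a way to measure incretin secretion after calories, and the Appendix worksheet measures GLP-1, CCK, PYY, amylin, GIP and ghrelin around that meal. The trial is open label, everyone enrolled receives ARD-101, and there is no undosed fasting series at 0, 1 and 2 hours. A fed 2-hour value could therefore be read as a drug response. Without a record of first food, the analyst could not tell afterwards which samples were affected.

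**Working it through.** The plan states no figure to reproduce. The check is clock arithmetic.

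**Inputs**
- Dose at t = 0.
- Dose-to-breakfast interval: about 60 min (section 4.1).
- Post-dose draws: +60 and +120 min (section 8.2.11; section 3.3; Table 1 footnote d).

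**Formula:** draw time relative to breakfast = draw time after dose - dose-to-breakfast interval.

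**If section 4.1 is followed on Day 1**
- 1-hour draw: 60 - 60 = about 0 min, that is, at breakfast.
- 2-hour draw: 120 - 60 = about 60 min after breakfast starts.

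**Allowing for the word approximately.** The tolerances are assumptions, as the protocol gives none.

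| Tolerance on 60 min | Breakfast after dose | 1-hour draw relative to breakfast | 2-hour draw after breakfast |
|---|---|---|---|
| ±15 min | 45 to 75 min | 15 min before to 15 min after | 45 to 75 min |
| ±30 min | 30 to 90 min | 30 min before to 30 min after | 30 to 90 min |

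The 2-hour draw is after food throughout both ranges. The 1-hour draw is at risk only if breakfast starts before the sample is taken.

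**If section 8.2.11 is followed on Day 1**
- Fasting at +120 min needs breakfast at 120 min or later, and 120 / 60 = 2, so at least twice the section 4.1 interval. That is outside either tolerance above.

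**Extent.** With about 30 subjects (section 4.1) there are 30 × 2 = 60 planned post-dose samples. The 2-hour set is 30 of them, or half. Section 9.9 gives 25 subjects instead, and the fraction is the same (25 of 50).

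**The case against.** The strongest reply is that section 8.2.11 is the specific text and section 4.1 the general one. Section 8.2.11, section 3.3 and the Table 1 row all call the samples fasting, and staff following 8.2.11 literally would keep the subject unfed through the second draw. The protocol also sets 4.1 aside on another procedure day: the Appendix worksheet gives the drug at -30 min before the second mixed meal, not -60. That worksheet is headed with a different study number (AARD-201), so it carries limited weight.

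This stands in part. A reader might infer that the 2-hour sample will be post-prandial. The documents do not support that; they show two instructions in conflict and no rule of precedence. Section 10.7 says the protocol is to be followed exactly, which on this point is impossible.

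A second reply is that drug-free meal data exist. On the undosed run-in day the worksheet samples GLP-1, CCK, PYY, amylin, GIP and ghrelin at -15, 120 and 240 min around a standard meal. This also stands in part: the series gives within-subject information on the meal response, but it has no draw of these hormones at 60 min after the meal and is not an undosed fasting series at the Day 1 times.

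A third is that the consequences are small. The endpoint is exploratory, the study is summarised descriptively and not powered (sections 9.2 and 9.9), and section 9.8 leaves exploratory detail to the SAP. That is right about weight. It does not remove the conflict, because an analysis plan cannot recover meal times that were never recorded.

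**Conclusion.** The inconsistency is real and limited. Section 4.1 and the fasting requirement in sections 8.2.11 and 3.3 and Table 1 cannot both hold on Day 1. If 4.1 governs, the 2-hour sample is about 60 minutes after breakfast (30 to 90 minutes under the widest tolerance assumed), and a meal response could be mistaken for a drug effect. If 8.2.11 governs, the sample is valid and 4.1 is breached.

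It affects one of two post-dose timepoints of one exploratory endpoint. The primary weight endpoint and the secondary endpoints are untouched, and the 1-hour sample remains usable if drawn before food.

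Two stronger readings go too far. A reader might infer that the whole hormone panel is biased in the drug's favour, but the documents give neither size nor direction for a meal effect and do not show that every analyte, such as leptin or adiponectin, would respond within an hour. A reader might also expect differences between sites, but this is a single-center study; only variation between subjects is possible.

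**What to change.** - Reconcile section 4.1, section 8.2.11 and Table 1 footnotes d and e for Day 1, so that one stated sequence of dose, draws and first food applies to every subject. Which timing applies is for the sponsor to decide.
- Record on the Day 1 form the clock times of the dose, each draw and first food.
- State in the analysis plan that only samples drawn before first food enter the fasting endpoint, and that any later sample is reported separately as post-prandial.

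The cost is a short text change and additional time entries on one form. The possible loss is a smaller number of 2-hour samples in the fasting endpoint, depending on the sequence chosen.

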8.2.12. Fecal Microbiome Analysis

All subjects of the study will optionally provide their fecal samples during the run-in visit and on day 28 for microbiome analysis to evaluate potential effects of the study medication on fecal microbiome profile (Table 1).

8.2.13. Non-invasive Phenotypic Bitter Taste Test

All subjects of the study will optionally undergo a non-invasive phenotypic bitter taste test using commercialized phenylthiocarbamide (PTC) and 6-n-propylthiouracil (PROP) taste strips, and a commercialized Allegro Bitrex[®] Fit Test Kit during the run-in visit of the study (Table 1). This data can be used to retroactively assess a correlation of bitter taste sensitivity of subjects with the efficacy of the study medication.

9. STATISTICAL CONSIDERATIONS

9.1. Study Population

9.1.1. Protocol Deviations

Important protocol deviations will be listed by subject.

9.2. General Considerations

Continuous data will be summarized using descriptive statistics (number, mean, standard deviation [SD], minimum, median and maximum). Categorical data will be summarized using frequency tables (number and percentage).

9.3. Subject Disposition

Subjects excluded from the safety analysis sets will be listed including the reason for exclusion. Subject disposition will be summarized and will include the following information: number of subjects dosed, number and percentage of subjects completing the study and the number and percentage of subjects who were withdrawn (including reasons for withdrawal). Disposition data will be presented based on all.

Subject discontinuations will be listed including the date of study exit, duration of treatment and reason for discontinuation. A listing of informed consent response will also be presented.

9.4. Demographic and Anthropometric Information and Baseline Characteristics

Demographic and anthropometric variables (age, sex, ethnicity, race, height, body weight and BMI) will be listed by subject. Demographic characteristics (age, sex, ethnicity and race) and anthropometric characteristics (height, body weight, and BMI) will be summarized for all subjects in the safety analysis set. The denominator for percentages will be the number of subjects in the safety analysis set for each treatment or for all subjects as applicable.

Medical history data will be listed by subject including visit, description of the disease/procedure, MedDRA system organ class (SOC), MedDRA preferred term (PT), start date, and stop date (or ongoing if applicable).

9.5. Prior and Concomitant Medication and Drug Administration

Prior medications are those that started and stopped prior to the first dose of study medication. Concomitant medications are those taken after first dosing (including medications that started prior to dosing and continued after).

Prior and concomitant medication will be listed by subject and will include the following information: reported name, PT, the route of administration, dose, frequency, start date/time, duration and indication.

Prior and concomitant medication will be coded according to the World Health Organization Drug Dictionary (WHO-DD) latest version.

Drug administration dates and times will be listed for each subject.

9.6. Exposure

A listing of drug administration will be created and will include the date and time of administration.

9.7. Safety Analyses

Where applicable, pre-dose measurements on Day 1 are considered baseline values for safety variables.

9.7.1. Adverse Events

All AEs will be listed. The number and percent of subjects experiencing an event will be tabulated for each SOC and PT. The AEs will also be tabulated according to intensity and causality. A TEAE is defined as an AE with a start date on or after the first dose of study drug, or that worsened following first administration of study drug. For purposes of data analysis, the end of the TEAE period will be the last time point when a subject was evaluated for AEs.

The AEs (TEAEs) will be tabulated according to intensity and causality, as applicable.

Non-TEAEs will be listed, as applicable.

Serious AEs will be listed separately.

9.7.2. Clinical Laboratory Tests

Individual data listings of laboratory results will be presented for each subject. Flags will be attached to values outside of the laboratory's reference limits along with the Principal

Investigator's assessment or designee. Clinically significant laboratory test abnormalities that were considered AEs by the Principal Investigator will be presented in the AE listings.

Clinical laboratory tests (observed values) will be summarized descriptively in tabular format. Shift tables will be presented for select laboratory parameters.

9.7.3. Vital Signs

Individual data listings of vital signs (observed and change from baseline) will be presented for each subject. Individual clinically significant vital signs findings that were considered AEs by the Principal Investigator will be presented in the AE listings.

Observed values as well as change from baseline data will be summarized descriptively in tabular format.

9.7.4. Standard 12-lead Electrocardiogram

Standard 12-lead ECG data (observed and change from baseline) will be listed for each subject and time point. Observed values will be summarized descriptively in tabular format. Change from baseline will be summarized descriptively for QTc data. A categorical QTc analysis will also be performed.

9.7.5. Physical Examination

Abnormal physical examination findings will be listed.

9.8. Exploratory analysis

Exploratory analysis may be presented separately from the main clinical study report (CSR). Further details on exploratory analyses will be provided in the SAP.

9.9. Determination of Sample Size

The determination of sample size is not based on statistical considerations of power but 25 subjects is considered sufficient to meet the study objectives.

10. ETHICAL, LEGAL AND ADMINISTRATIVE ASPECTS

10.1. Data Quality Assurance

The Sponsor or designee will conduct a study initiation visit to verify the qualifications of the Principal Investigator, inspect the facilities and inform the Principal Investigator of responsibilities and procedures for ensuring adequate and correct documentation.

The Principal Investigator must prepare and maintain adequate and accurate records of all observations and other data pertinent to the clinical study for each study participant. Frequent communication between the clinical site and the Sponsor is essential to ensure that the safety of the study is monitored adequately. The Principal Investigator will make all appropriate safety assessments on an ongoing basis. The Medical Monitor may review safety information as it becomes available throughout the study.

All aspects of the study will be carefully monitored with respect to Good Clinical Practice (GCP) and SOPs for compliance with applicable government regulations. The Study Monitor will be an authorized individual designated by the Sponsor. The Study Monitor will have access to all records necessary to ensure integrity of the data and will periodically review the progress of the study with the Principal Investigator.

10.2. Data Collection and Access to Source Data/Documents

The Principal Investigator will ensure the accuracy, completeness and timeliness of the data reported to the Sponsor. The Investigator or designee will cooperate with the Sponsor's representative(s) for the periodic review of study documents to ensure the accuracy and completeness of the data at each scheduled monitoring visit. Data clarification requests will be provided to the study team by means of electronic or manual queries.

The Investigator will allow Sponsor representatives, contract designees, authorized regulatory authority inspectors and the IEC to have direct access to all electronic records pertaining to the study.

All data should be recorded, handled and stored in a way that allows its accurate reporting, interpretation and verification.

10.3. Archiving Study Documents

All source documents generated in connection with the study will be retained in the limited access file storage area, respecting the privacy and confidentiality of all records that could identify the

subjects. Direct access is allowed only for authorized people for monitoring and auditing purposes. Source documents will be handled, stored and archived according to in-house procedures.

The Investigator's Site File will be archived by the CRO for at least 2 years after completion of the study or longer if agreed upon by the Sponsor.

10.4. Good Clinical Practice

The procedures set out in this clinical study protocol are designed to ensure that the Sponsor and the Principal Investigator abide by the principles of the ICH guidelines on GCP. The clinical study also will be carried out in keeping with national and local legal requirements (in accordance with United States investigational new drug [IND] regulations [21 CFR 56]).

10.5. Informed Consent

Eligible subjects may only be included in the study after providing IRB/IEC approved informed consent.

Informed consent must be obtained from the subject before conducting any study-specific procedure.

As part of the informed consent procedure, the Principal Investigator or designee must explain orally and in writing the nature, duration and purpose of the study and the action of the drug in such a manner that the subject is aware of the potential risks, inconveniences or AEs that may occur. The subject should be informed that he/she is free to withdraw from the study at any time. Subjects will receive all information that is required by federal regulations and ICH guidelines. The ICF must be signed and dated; one copy will be handed to the subject, and the Principal Investigator will retain a copy as part of the clinical study records. The Principal Investigator will not undertake any investigation specifically required for the clinical study until written consent has been obtained. The terms of the consent and when it was obtained must be documented in the subject source documents.

The Sponsor will review the Investigator-proposed ICF to ensure it complies with the ICH GCP guideline (including the ethical principles that have their origins in the Declaration of Helsinki) and regulatory requirements and is considered appropriate for this study. The Principal Investigator or designee will provide the Sponsor with a copy of the IRB/IEC approved ICF prior to the start of the study.

If a protocol amendment is required, then the ICF may need to be revised to reflect the changes to the protocol. If the ICF is revised, it must be reviewed and approved by the responsible IRB/IEC and signed by all subjects subsequently enrolled in the clinical study, as well as those currently enrolled in the clinical study as applicable.

